4.7 Analysis methods

4.7.1 Study population

4.7.1.1 Patient disposition

The disposition of patients for the pre-treatment period and the double-blind treatment period will be summarised. This involves all patients enrolled (who signed informed consent) in the pre-treatment period; all patients randomised to the double-blind treatment period (and those not randomised and reason for not randomised); all patients completing (and discontinuing and reasons for discontinuing) the double-blind treatment period.

4.7.1.2 Demographic and baseline characteristics

Demographic and other baseline characteristics, including diabetes-related characteristics and renal function characteristics, will be summarised and listed by treatment group and overall, using the Randomised Patients Set.

Table 7 describes the demographic and baseline characteristics; Table 8 describes the diabetes-related common baseline characteristics and Table 9 describes the common renal function baseline characteristics.

Table 7. Demographic and baseline characteristics

Characteristic	Туре	Categories
Gender	Categorical	Male, Female
Age	Continuous and categorical	< 65 yrs; ≥65 - <75 yrs; ≥75 yrs

Date 21 Mar 2017		
Female age	Categorical	≤50 yrs; >50 yrs
Race	Categorical	White; Black or African
		American; Asian; Other
Ethnicity	Categorical	Hispanic/Latino, Not
		Hispanic/Latino
Body weight	Continuous	
Height	Continuous	
Waist circumference	Continuous	
Body Mass Index	Continuous and categorical	$<25 \text{kg/m}^2; \ge 25 \text{kg/m}^2; \ge 27 \text{kg/m}^2;$ $\ge 30 \text{kg/m}^2$
Country	Categorical	Germany; Slovakia; Hungary;
		Poland; Czech Republic

Table 8. Diabetes-related baseline characteristics

Characteristic	Туре	Categories
Duration of type 2 diabetes	Continuous and categorical	$< 3 \text{ yrs}; \ge 3 - \le 10 \text{ yrs}; > 10 \text{yrs}$
HbA1c	Continuous and categorical	<8%; ≥8% - <9%; ≥9%
FPG	Continuous	
C-Peptide	Continuous	

Table 9. Baseline renal function and other characteristics

Characteristic	Type	Categories
eGFR (MDRD)	Categorical and continuous	<30 mL/min/1.73 m ² ; ≥30 - <45
		$mL/min/1.73 \text{ m}^2; \ge 45 - < 60$
		$mL/min/1.73 \text{ m}^2; \ge 60 - < 90$
		mL/min/1.73 m ² ;
		≥90 mL/min/1.73 m ²

4.7.1.3 Specific and general disease histories

The number (percent) of patients with diabetes and diabetes-related disease histories will be summarised and listed by treatment group, and overall using the Randomised Patients Set.

The number (percent) of patients with abnormal general medical history findings will be summarised by treatment group and overall by System Organ Class (SOC) and Preferred Term (PT) using the Randomised Patients Set. Medical History will be coded using the MedDRA dictionary (version 19.1 or later).

4.7.2 Extent of exposure

4.7.2.1 Study medication

The extent of exposure to study medication (investigational products) during the double-blind treatment period is defined as the difference between the last and the first dose of study medication of the double-blind treatment period plus 1 day.

The extent of exposure to study medication will be summarised using the Safety Analysis Set. The number and percent of patients with an extent of exposure within pre-specified day ranges will be presented for the double-blind treatment period by treatment group as follows: 1-6; 7-14; 15-28; 29-42; 43-56; 57-70; 71-84; 85-168; 169-252; 253-336; 337-371, ≥372 days. The mean, standard deviation (SD), median and range of the number of days of exposure will also be presented.

A listing of patients by batch number of study medication will be generated.

Dose levels of metformin at randomisation (visit 2) will be summarised for each treatment group (Safety Analysis Set). Dose levels of glimepiride at week 52 and over time will be summarised for this treatment group (Safety Analysis Set).

4.7.2.2 Interruption of study medication

Dates for any interruptions of study drug will be captured on the Exposure (EX) CRF page. Dose interruptions will be summarised for each treatment group (Safety Analysis Set). Down titrations to 0mg glimepiride will be included as interruptions (for the purposes of this summary table only).

4.7.2.3 Dose titrations of Glimepiride

The number of patients with a down-titration will be summarised for the glimepiride plus metformin treatment group (Safety Analysis set).

4.7.3 Current and Concomitant medications

Current and concomitant medications will be summarised using the Safety analysis set by drug class (anatomic class and therapeutic class), generic drug name and treatment group, as defined by the AstraZeneca Drug Dictionary most current at time of database lock (version 16.2 or later). A summary will be produced for each of the following:

- all current medication
- all concomitant medication

Current medications are defined as medications with a start and stop date prior to the first day of double-blind treatment, i.e. current medication will be any medication with at least 1 dose taken on or after the day of consent date up to the day prior to the first dose of study medication and stopped prior to the first dose of study medication.

Concomitant medications are defined as a medication with either:

- a recorded medication start date falling within the double-blind treatment period (i.e. a medication started during the double-blind phase), or
- a recorded medication start date prior to the first day of study medication during the double-blind treatment period without any recorded medication stop date prior to the start of the double-blind treatment period (i.e. a medication started prior to double-blind medication and continued in the double-blind phase).

If missing or partial dates of medication start/stop dates occur, the medication will be assumed to be taken during the double-blind treatment period unless there is convincing evidence to the contrary, i.e. it will be included in the summary table of concomitant medications.

4.7.3.1 Other Treatments

A list of the prohibited medications during the study (and their corresponding time frames) is presented in Table 10.

Table 10. List of prohibited medications

Restricted Medication/Class of drug:	Usage
Sulfonylureas, pioglitazone, rosiglitazone, GLP-1 receptor agonists, any DPP-4 and SGLT2 inhibitors other than IP.	Prohibited during the study.
Insulin therapy (with the exception of insulin therapy during a hospitalisation or use in gestational diabetes).	Use of insulin during the study is only acceptable if given as a rescue treatment as allowed per the protocol (CSP Section 7.8.2) for any duration as clinically necessary, or for a temporary use in the following situations:
	- For up to 14 days in total and up to 7 consecutive days if patient is unable to take oral medications
	- For up to 14 days in total and up to 7 consecutive days if there is a documented illness or infection that requires additional therapy to maintain glycaemic control
	 For up to 14 days in total and up to 7 cconsecutive days if patients have to temporarily stop study medication or metformin due to recommendations made in this protocol For up to 7 days during hospitalization. When the reason for hospitalisation is the management of the patient's glycaemic control, treatment with insulin is considered a rescue and is allowed for as long as clinically necessary

Restricted Medication/Class of drug:	Usage
Other investigational drugs or participation in any interventional clinical study	Prohibited during the study.
Treatment with systemic glucocorticoids equivalent to oral prednisolone ≥10 mg (betamethasone ≥1.2 mg, dexamethasone ≥1.5 mg, hydrocortisone ≥40 mg) per day	Newly initiation of treatment with any systemic corticosteroid therapy that will involve ≥5 days of therapy (inhaled and topical are allowed). The Medical Monitor should be consulted prior to beginning therapy with corticosteroids for patients who require systemic corticosteroid treatment.
Prescription or over-the-counter weight loss medications	Prohibited during the study.

Other treatments include:

Metformin

Patients will remain on their pre-study stable, maximum tolerated metformin doses ≥ 1500 mg/day, during the 52-week double-blind treatment period of the study. Metformin should be administered and stored according to product and country-specific labelling.

Metformin will not be provided in pre-packaged kits by the Sponsor as it is the usual care prior to study participation.

• Rescue therapy

Patients may be eligible for rescue therapy with open-label rescue medication (Insulin) for treating ongoing hyperglycaemia. Patients should continue receiving blinded study medication while receiving rescue therapy. If rescue therapy fails, further therapy will be given at the discretion of the Investigator.

Rescue therapy will be prescribed by the investigator (and not provided by the Sponsor).

• Other concomitant treatment

Other medication other than that described above, which is considered necessary for the patient's safety and well-being, may be given at the discretion of the investigator and recorded in the appropriate sections of the CRF.

4.7.4 Treatment compliance

Percent treatment compliance will be calculated during the double-blind treatment period for each treatment group. For each patient, percent compliance is defined as the number of tablets taken divided by the number of tablets that should have been taken, multiplied by 100.

The number of tablets that should have been taken will be calculated as the double-blind treatment stop date – double-blind treatment start date + 1, multiplied by 4 (since each patient should take 1 tablet per day from each of the 4 bottles).

The number of tablets taken will be calculated as the total number of tablets dispensed minus the total number of tablets returned (i.e. the totals for all 4 bottles).

A patient is considered compliant if percent compliance is \geq 80% and \leq 120%. The number and percent of patients considered compliant will be summarised for each treatment group using the Safety Analysis Set.

4.8 Efficacy analyses

The following table provides a summary of how each efficacy variable will be analysed:

Table 11 Statistical analyses to be conducted and sensitivity analyses

Efficacy Variable	Analyses
Primary:	
Change in HbA1c from baseline to week 52	Primary analysis:
	MMRM (Full Analysis Set)
	Sensitivity analyses:
	MMRM (Per Protocol Analysis Set)
	ANCOVA using values prior to rescue treatment (LOCF used if the week 52 value is not available)
	MMRM primary model repeated including all values regardless of whether patient used rescue treatment or discontinued treatment
	Subgroup analyses:
	MMRM with covariates for each of the following: age group, gender, race, country, baseline HbA1c and baseline eGFR
Key Secondary:	
Proportion with at least one episode of confirmed hypoglycaemia	Logistic regression
Change in body weight from baseline to week 52	MMRM
Change in FPG from baseline to week 52	MMRM
Time to rescue	Cox PH model
Other Secondary:	
Proportion achieving HbA1c <7% (and <7.5%) without confirmed hypoglycaemia at week 52	Logistic regression

Proportion achieving HbA1c <7% (and <7.5%) Logistic regression

at week 52

Proportion achieving individually agreed HbA1c Logistic regression

targets at week 52

Proportion with an HbA1c decrease of ≥1% with Pearson's Chi-square test

no weight gain at week 52

Time spent below HbA1c target (<7% and ANCOVA

<7.5%)

Change in BMI from baseline to week 52 ANCOVA (LOCF)

Proportion with a weight reduction ≥5% or a Logistic regression

weight gain $\geq 5\%$ at week 52

Proportion with at least 1 episode of any

Logistic regression

hypoglycaemia

Change in waist circumference from baseline to ANCOVA (LOCF)

week 52

Change in systolic BP from baseline to week 52 MMRM

Proportion with at least one episode of Logistic regression hypoglycaemia (symptomatic with blood

glucose \leq 70 mg/dL [3.9mmol/L])

Note: Each analysis is based on the Full Analysis Set unless otherwise stated.

4.8.1 Primary Efficacy Analysis

The primary efficacy variable is the change in HbA1c from baseline to week 52 in the double-blind treatment period. The primary efficacy analysis will be based on the Full Analysis Set including values prior to rescue treatment or discontinuation. Values recorded after rescue treatment for those patients who used rescue medication or values collected more than 8 days after last dose date for patients who stayed more than 8 consecutive days off treatment are excluded from the analysis.

The primary efficacy variable will be analysed using the MMRM model (Section 4.5.4) with fixed effects for treatment group and covariates (baseline HbA1c; week (week 2 to week 52), and interactions baseline HbA1c-by-week and treatment group-by-week). Point estimates and 95% CIs will be calculated for the adjusted mean changes from baseline within each treatment group as well as for each comparison versus control in adjusted mean changes. The Kenward-Roger approximation will be used to estimate denominator degrees of freedom (DDFM) while an unstructured variance will be used to model the within-patient errors.

The primary assessments of efficacy will be a comparison of each of the 2 test groups: the dapagliflozin plus saxagliptin added to metformin versus the control group (glimepiride added to metformin) - and the dapagliflozin added to metformin versus the control group - using a 2-sided 95% CI. In particular, if the observed upper limit from a 2-sided 95% CI for the

difference in adjusted means is less than 0.30%, then the test group will be considered to be non-inferior to the control group.

Multiplicity will be controlled using a sequential testing scheme: the dapagliflozin plus saxagliptin added to metformin group will be tested versus the glimepiride group first, followed by the dapagliflozin plus metformin group versus the glimepiride group. If the first comparison is non-inferior the second comparison will be tested. Otherwise, significance testing will stop at the first comparison and the second comparison will be reported descriptively. See Section 4.2.1 for details. A superiority test of the dapagliflozin plus saxagliptin added to metformin group versus the glimepiride added to metformin group will also be conducted using the same modelling approach as for the primary non-inferiority analysis.

4.8.2 Analysis of secondary and exploratory variables

All secondary endpoints will be analysed using the Full Analysis set including values prior to rescue treatment or discontinuation. For HbA1c, weight, BMI and waist circumference, values recorded after rescue treatment for those patients who used rescue medication or values collected more than 8 days after the last dose date for patients who stayed more than 8 consecutive days off treatment are excluded from the analysis. For FPG, values recorded after rescue treatment for those patients who used rescue medication or values collected more than 1 day after the last dose date for patients who stayed more than 1 consecutive day off treatment are excluded from the analysis. For SBP, values recorded after rescue treatment for those patients who used rescue medication or values collected more than 4 days after the last dose date for patients who stayed more than 4 consecutive days off treatment are excluded from the analysis.

The statistical testing of the primary and key secondary efficacy variables will proceed in a sequential manner. If for the primary comparison between dapagliflozin or dapagliflozin plus saxagliptin (added to metformin) treatment group and the glimepiride (added to metformin) treatment group, the upper limit from a 2-sided 95% CI for the difference in adjusted means is less than 0.30%, then the dapagliflozin or dapagliflozin plus saxagliptin will be non-inferior to glimepiride and all four key secondary efficacy variables will be tested for superiority at a 0.05 level (two-sided) as well as the superiority test of the primary efficacy variable. To protect the type I error rate of the hierarchical testing procedure, the interpretation of the statistical significance of treatment comparisons for each key secondary efficacy variable and the superiority test of the primary efficacy variable will be done using a step-wise procedure (described in Section 4.3.1).

A summary of each efficacy variable and associated analysis is provided in Table 11.

The analysis of the changes from baseline to week 52 for a) total body weight, b) FPG and c) SBP will be performed using the MMRM model (as described for the primary efficacy endpoint). Point estimates and 2-sided 95% CI will be calculated for the adjusted mean changes from baseline within each treatment group and between treatment groups together with the p-values corresponding to testing the hypotheses of no difference between

dapagliflozin added to metformin and dapagliflozin plus saxagliptin added to metformin compared to glimepiride added to metformin.

The time spent below HbA1C target (<7% and <7.5%) from baseline to week 52 will be analysed using an analysis of covariance (ANCOVA) model with fixed effects for treatment group and baseline HbA1c (see section 4.5.5). The change from baseline at week 52 in a) BMI and b) waist circumference will be analysed using an ANCOVA model with fixed effects for treatment groups and respective baseline covariates (see section 4.5.5). LOCF will be applied as detailed in section 4.6.2 for the latter two analyses. The ANCOVA model will be used to derive a least squares estimate of each test drug combination versus the control with 95% CI and (a corresponding 2-sided) p-value. In addition, a 2-sided 95% CI for the mean change within each treatment group will be calculated.

Time to rescue will be analysed using a Cox proportional hazards model with the Efron method (Ref 2) for handling ties (i.e., same rescue times). Estimates of the hazard ratio and 95% CI will be provided. Kaplan-Meier estimates will be calculated and plotted by treatment group. Median time to rescue and their 95% CIs (derived from the Kaplan-Meier estimates) will also be reported. Patients will be censored at the final visit (Visit 12; week 52) if rescue has not occurred by then (Section 4.5.6), or will be censored at the time of insulin start (for those subjects who received rescue treatment without confirmed rescue criteria). The proportional hazards (PH) assumption of the Cox model will be visually checked (e.g., the survival curves should not cross for the PH to hold). If the PH assumption is not met, the time to rescue will be analysed using a Wilcoxon test (using SAS proc lifetest).

The proportion of patients with at least one episode of confirmed hypoglycaemia, the proportion achieving HbA1c <7% (and <7.5%) without confirmed hypoglycaemia at week 52, the proportion achieving HbA1c <7% (and <7.5%) at week 52, the proportion achieving their individually agreed HbA1c targets at week 52, the proportion with at least one episode of any hypoglycaemia and the proportion with at least one episode of hypoglycaemia (symptomatic with blood glucose ≤70mg/dL [3.9mmol/L]) will be summarised by treatment group and compared between treatment groups using logistic regression with baseline HbA1c as a covariate (see section 4.5.7). The adjusted percentage with 95% CI, Odds Ratio with 95% CI and nominal p-values for the comparison of dapagliflozin or dapagliflozin plus saxagliptin vs glimepiride will be presented. The confidence intervals will be based on the profile likelihood method.

The proportion of patients achieving a \geq 5% weight reduction or \geq 5% weight gain will be summarised by treatment group and compared between treatment groups using logistic regression with baseline weight as a covariate.

The proportion of patients with an HbA1c decrease ≥1% with no weight gain at week 52 will be summarised by treatment group and comparisons between treatment groups (contrasts of each test combination vs the control) will be performed using a Pearson's Chi-Square test. Nominal p-values and asymptotic 95% CIs will be presented.

Descriptive summaries of change from baseline in HbA1c, FPG, weight, BMI, waist circumference and systolic BP over time (observed values), will be presented in addition to the analyses described above.

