4.2.1 Objectives and hypotheses

The combination of metformin and a sulphonylurea (glimepiride) is a standard therapy in the treatment of type 2 diabetes and has been shown to reduce HbA1c.

The primary objective of this study is to demonstrate the non-inferiority of dapagliflozin and dapagliflozin plus saxagliptin as add-on therapies to metformin compared to glimepiride as add-on therapy to metformin for the primary efficacy variable (change in HbA1c from baseline to week 52).

The null hypothesis H_0 (given below) will be tested against the alternative hypothesis H_A ($\alpha = 0.025$, one-sided):

$$H_0$$
: $\mu_t - \mu_c \ge 0.30\%$,

$$H_A$$
: $\mu_t - \mu_c < 0.30\%$

where μ_t denotes the mean absolute change in HbA1c from baseline to week 52 in patients treated with dapagliflozin added to metformin and dapagliflozin plus saxagliptin added to metformin (test medication); μ_c denotes the mean absolute change in HbA1c from baseline to week 52 in patients treated with glimepiride added to metformin (active control). The non-inferiority margin is determined to be 0.30% (in absolute terms). A difference of 0.30% or

less, in HbA1c change from baseline to week 52 between the treatment groups, is considered clinically equivalent (from a medical point of view). Non-inferiority will be assessed using the 2-sided 95% Confidence Interval (CI) of the adjusted mean difference between dapagliflozin or dapagliflozin plus saxagliptin and glimepiride. If the upper limit of the 2-sided 95% CI is less than 0.30% then dapagliflozin or dapagliflozin plus saxagliptin will be considered to be non-inferior to glimepiride.

To preserve the Type I error \leq 0.025 (one-sided), a hierarchical testing procedure will be used as follows:

- First test dapagliflozin plus saxagliptin versus glimepiride
- If non-inferiority is achieved then test dapagliflozin versus glimepiride

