4.3.1 Control of Type I error

The experiment-wise type I error will be controlled to a maximum of 5%. A hierarchical closed testing procedure will be employed such that key secondary endpoints will be considered for statistical significance (in terms of superiority) only if non-inferiority of the primary endpoint is concluded and that a key secondary endpoint will be considered for statistical significance only if the test ordered before it is found to be statistically significant. At each step, dapagliflozin plus saxagliptin added to metformin versus glimepiride added to metformin will be tested first followed by the test for dapagliflozin added to metformin versus glimepiride added to metformin except for the superiority tests of the primary endpoint and the endpoint of total body weight. The test of superiority for HbA1c will include only the comparison of dapagliflozin plus saxagliptin added to metformin versus glimepiride added to metformin. For total body weight, dapagliflozin added to metformin versus glimepiride will

be tested first followed by dapagliflozin plus saxagliptin added to metformin versus glimepiride added to metformin.

The following testing order will be followed for the overall type I error control:

- 1. Change from baseline in HbA1c at Week 52 (test for non-inferiority)
- 2. Proportion of patients reporting at least 1 episode of confirmed hypoglycaemia at Week 52 (test for superiority)
- 3. Change in total body weight from baseline to Week 52 (test for superiority)
- 4. Change from baseline in HbA1c at Week 52 (test for superiority of dapagliflozin plus saxagliptin added to metformin vs glimepiride added to metformin only)
- 5. Change in FPG from baseline to Week 52 (test for superiority)
- 6. Time to rescue at Week 52 (test for superiority)

The statistical comparisons will be done using a comparison-wise type I error of 5% (2-sided). For all other secondary variables and exploratory variables, nominal p-values will be reported without multiplicity controlled significance testing.

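### The 'or' gate to the key secondary tests in SAP 4.8.2 conflicts with the single fixed sequence of 4.3.1, and leaves open what happens if the combination is non-inferior but dapagliflozin is not

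*SAP*

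**What the plan says.** Four sections of the SAP govern the order of testing.

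- **4.2.1 and 4.8.1** order the two non-inferiority comparisons on HbA1c: dapagliflozin plus saxagliptin (D+S) against glimepiride, then dapagliflozin (D) against glimepiride. In 4.8.1, "If the first comparison is non-inferior the second comparison will be tested"; if it is not, "significance testing will stop at the first comparison and the second comparison will be reported descriptively".
- **4.3.1** states that "The experiment-wise type I error will be controlled to a maximum of 5" per cent. The key secondary endpoints are considered "only if non-inferiority of the primary endpoint is concluded", and "a key secondary endpoint will be considered for statistical significance only if the test ordered before it is found to be statistically significant". The steps are listed by endpoint: HbA1c non-inferiority, confirmed hypoglycaemia, body weight, HbA1c superiority, FPG, time to rescue. Within a step D+S comes before D, except that D comes first for weight and the HbA1c superiority step has the D+S comparison only.
- **4.8.2** restates the entry condition for either test arm. Once the upper limit lies under the 0.30% margin, it reads: "then the dapagliflozin or dapagliflozin plus saxagliptin will be non-inferior to glimepiride and all four key secondary efficacy variables will be tested for superiority". The level given for these tests is two-sided 0.05. The sentence after it hands the interpretation of significance to the step-wise procedure of 4.3.1, to protect the type I error.

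**The concern.** The gate in 4.8.2 is worded with 'or', so one non-inferior arm would be enough to open the secondary tests. A single fixed sequence needs both non-inferiority tests to succeed before the third test is reached.

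The cross-reference to 4.3.1 does not fully settle this. Five of the six steps there hold two comparisons. The text speaks of non-inferiority of the primary endpoint without saying for which arm, and its advance rule speaks of an endpoint in one half of the sentence and a test in the other. It does not say what becomes of the later steps when one comparison in a step succeeds and the other does not.

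At stake is whether superiority claims on hypoglycaemia, weight, HbA1c, FPG and time to rescue are confirmatory or nominal. If the two arms split, that question would be settled after unblinding by choosing which section to follow.

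**Working it through.** **1. The plan's own figure.** Inputs from SAP 1.3: margin 0.30%, SD 1.0%, one-sided 0.025, true difference zero, 290 evaluable per arm.

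- n per arm = 2 × 1.0² × (1.960 + 1.645)² / 0.30² = 288.8, so 289. The plan uses 290.
- SE = √(2/290) = 0.0830. Power = Φ(0.30/0.0830 − 1.960) = Φ(1.653) = 0.951.

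The 290 and the 95% are reproduced. The point does not touch the sample size.

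**2. The outcomes of the primary step.**

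| D+S | D | 4.8.1 and 4.3.1, read strictly | 4.8.2 gate, read literally |
|---|---|---|---|
| fails | not tested | stop (4.8.1 is explicit) | opens nothing, because D is only reported descriptively |
| passes | passes | go on | go on |
| passes | fails | stop, since the test ordered before D+S hypoglycaemia has failed | go on |

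Only the last row gives opposite answers.

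**3. Chance of that row at the primary step.** The two comparisons share the glimepiride arm, and 1:1:1 allocation (SAP 1.2.2) gives a correlation of 0.5. With zero true difference for both arms, each comparison fails with probability 1 − 0.951 = 0.049. The bivariate normal probability that both miss is 0.012. So

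P(D+S passes, D fails) = 0.049 − 0.012 = 0.037, about 4%.

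D+S fails first with probability 0.049, the case that 4.8.1 already settles.

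**4. Familywise error in that row.** Take D exactly at the margin (its non-inferiority null is true), D+S clearly non-inferior, and D+S with no effect on confirmed hypoglycaemia (its superiority null is true).

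- *Strict chain:* D+S hypoglycaemia is reached only after D has been falsely declared non-inferior. The error is 0.025.
- *Testing goes on:* either of two true nulls can be rejected. If the two statistics are independent, the one-sided error is 1 − 0.975² = 0.0494. With the superiority test counted two-sided it is 1 − 0.975 × 0.95 = 0.0738.

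The SAP gives no correlation between endpoints, so it was varied as an assumption. With the arm correlation of 0.5, simulation of 1,000,000 trials per setting gave:

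| Correlation between endpoints | Strict, one-sided | Going on, one-sided | Going on, superiority test two-sided |
|---|---|---|---|
| 0 | 0.025 | 0.050 | 0.074 |
| 0.3 | 0.025 | 0.048 | 0.073 |
| 0.5 | 0.025 | 0.048 | 0.073 |

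Continuation therefore roughly doubles the one-sided error, and the result depends little on the assumed correlation.

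**The case against.** The strongest reply is that 4.8.2 ranks itself below 4.3.1. Its paragraph opens by calling the testing sequential, and the sentence after the gate sends interpretation to 4.3.1. The advance rule there refers to the preceding test, the arms are ordered within every two-comparison step, and the arm order is reversed for weight, which would have no purpose if each arm ran its own chain. The SAP also uses the same 'or' phrase elsewhere, for instance in 4.5.7, to mean each test arm in turn. All of this stands: one strict chain is the most natural reading of 4.3.1. It does not remove the fault, because 4.8.2 still states an entry condition that this chain contradicts, and 4.3.1 does not say that both arms are needed.

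A reader might infer more than the document supports:

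- *That error control fails whenever the arms split.* It does not. If D+S fails, 4.8.1 ends testing.
- *That the error reaches 8 to 10% (17 to 19% two-sided).* This needs a rule that a step is passed when either arm passes, applied through all the secondary endpoints. The SAP contains no such rule.
- *That the split is the likely way for the sequence to break, with a chance of 15 to 56%.* Those chances need a true advantage of 0.2% for the combination and a true disadvantage of 0.05 to 0.15% for dapagliflozin. The plan assumes zero for both, and then a failure of D+S (4.9%) is the more likely break at the primary step.

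**Conclusion.** The point holds as a conflict between two stated decision rules, with one case unresolved: D+S non-inferior and D not. It is not a demonstrated loss of error control, because the strict reading of 4.3.1 keeps the claimed level.

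If the 4.8.2 gate were followed in that case, the familywise error would be about 4.8 to 5.0% one-sided instead of 2.5%, or about 7.3 to 7.4% instead of 5% with the superiority test counted two-sided. These figures assume dapagliflozin at the margin, the combination null on hypoglycaemia, a correlation of 0.5 between arms, and 0 to 0.5 between endpoints. The two-sided figure also counts wrong-direction results, whereas 4.3 defines superiority by direction, so the one-sided figure is the closer measure of false claims.

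The chance of meeting the case at the primary step is about 4% under the plan's own assumptions. At the planned size and SD it becomes materially larger only if dapagliflozin is truly worse than glimepiride.

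**What to change.** In 4.8.2, delete the sentence with the 'or' gate and refer to 4.3.1 alone. In 4.3.1, replace the list by endpoint with one chain of 11 numbered tests (five steps × 2 comparisons + 1), in the order that section already implies:

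1. D+S, HbA1c non-inferiority
2. D, HbA1c non-inferiority
3. D+S, confirmed hypoglycaemia
4. D, confirmed hypoglycaemia
5. D, body weight
6. D+S, body weight
7. D+S, HbA1c superiority
8. D+S, FPG
9. D, FPG
10. D+S, time to rescue
11. D, time to rescue

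State that the first non-significant test ends confirmatory testing for both arms and that all later p-values are nominal. If the sponsor wants one arm to continue after the other has failed, specify an alpha split or a graphical procedure instead.

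The cost is a change of wording, to be made before unblinding; sample size and estimates are unaffected. The downside is that one arm's later claims are lost when the other arm fails earlier, which the strict reading of 4.3.1 already implies.
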